7. PHARMACOKINETICS/PHARMACODYNAMICS

7.1. Pharmacokinetics

Blood samples for pharmacokinetics (PK) will be collected at randomization and after randomization at Month 3, Month 6, and then every 6 months until Month 54. Collection at randomization is pre-dose, collection at post-randomization time points is both pre-dose and within 1 to 4 hours post-dose. For subjects participating in CSF collection, samples are collected during screening and post-randomization at Month 12 and Month 36 (and early termination if not collected at the previous visit). Concentrations below the limit of quantification (LOQ), will be treated as zero. No analysis is planned for PK parameters.

7.2. Pharmacodynamics

Biomarkers measured in this study include the following:

- Fluid biomarkers

- CSF: A subset of subjects will have longitudinal CSF samples taken during the study at randomization (if a CSF screening sample was taken, it was not necessary to have a repeat sample at randomization), Month 12, Month 36 (or early termination if not collected at the previous visit). After the biomarkers interim analyses (Section 3.1.1), the Month 12 sample could be taken any time between baseline and Month 36. The key parameter of interest is $A\beta_{1-40}$. $A\beta_{1-37}$, $A\beta_{1-38}$, $A\beta_{1-42}$, p-tau, and t-tau will also be measured.
- Imaging biomarkers
 - Amyloid PET: A subset of subjects will have longitudinal amyloid PET scans during the study at randomization (if an amyloid PET scan was performed during screening, it was not necessary to have a repeat scan at randomization), Month 24 and Month 48 (or early termination). The parameters of key interest are the composite region of interest (ROI) SUVR and regional SUVR's.
 - MRI: All subjects will have an MRI during screening and after randomization at Months 6, 12, 24, 36 and 54 (or early termination, if not performed at the previous visit). The parameters of key interest are brain volumes of the cortical and sub-cortical regions.

Biomarker analyses will be based only on those subjects with at least 85% treatment compliance (see Section 4.3) at the analysis time point.

Changes from baseline and percent changes from baseline will be calculated for all parameters.

Values of each parameter will be summarized with descriptive statistics at each time point by treatment group. Change from baseline will also be summarized for each parameter, at each time point by treatment group. Percent change from baseline in CSF and plasma $A\beta_{1-40}$ will be summarized at each time point by treatment group. Plots of mean (\pm SE) values, changes, and/or percent changes over time by treatment group will be provided for selected biomarkers.

For off-treatment visits, change and percent change from the off-treatment baseline (see Section 2.4) may also be calculated and summarized with descriptive statistics.

Exploratory evaluations of an association between biomarker data and changes in cognitive endpoints may be performed graphically with: 1) plots of biomarker results over time with mean (\pm SE) change score of the cognitive endpoints over time overlaid; 2) scatterplots of the change score of the cognitive endpoints versus baseline values of selected biomarkers by treatment group; and 3) scatterplots of the change scores of the cognitive endpoints versus changes in biomarkers by treatment group at corresponding time points.

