### **11.7. Biomarker Analyses**

Statistical analyses will be performed on the following:

- CSF A $\beta_{1-40}$  and plasma A $\beta_{1-40}$
- Amyloid PET parameters
- CSF p-tau
- Tau PET
- Volumetric and task-free functional MRI parameters

In addition to CSF A $\beta_{1-40}$  and CSF p-tau, alternate CSF markers of neurodegeneration will also be analyzed similarly. CSF analyses will be performed using the CSF analysis population.

For amyloid PET, the parameters of key interest will be the global composite ROI SUVR (eg, frontal, medial temporal, or parietal cortices; anterior and posterior cingulates) and regional SUVR (eg, cortical and subcortical ROIs). Amyloid PET analysis will be performed using the amyloid PET analysis population.

For tau PET, the parameters of key interest will be tau PET signal (SUVR) in ROI(s) known to accumulate substantial tau. The analyses will be performed using the tau PET analysis population.

For MRI, the parameters of key interest will be brain volumes of the cortical and sub-cortical regions.

The treatment effect will be estimated and compared with placebo. Details of the statistical methods will be provided in the SAP.

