## 4. Discontinuation of Study Treatment:

For subjects during the first 3 months of treatment with study drug, treatment must be discontinued if any of the following occurs:

- ALT or AST  $> 5 \times \text{ULN}$
- ALT or AST  $> 3 \times \text{ULN}$  and total bilirubin  $> 2 \times \text{ULN}$  or INR  $> 1.5$
- ALT or AST  $> 3 \times \text{ULN}$  with the appearance of fatigue, nausea, vomiting, right upper quadrant pain or tenderness, fever, rash, and/or eosinophilia  $> 5\%$

For subjects that have completed 3 months of treatment with study drug, treatment must be discontinued if any of the following occurs:

- ALT or AST  $> 8 \times \text{ULN}$

- ALT or AST  $> 5 \times \text{ULN}$  for more than 2 weeks
- ALT or AST  $> 3 \times \text{ULN}$  and total bilirubin  $> 2 \times \text{ULN}$  or INR  $> 1.5$
- ALT or AST  $> 3 \times \text{ULN}$  with the appearance of fatigue, nausea, vomiting, right upper quadrant pain or tenderness, fever, rash, and/or eosinophilia  $> 5\%$

5. SAE Reporting

Subjects who meet the criteria for discontinuation of study treatment should have the event reported as an SAE and should follow the SAE reporting process, as outlined in Section 12.3.2 of the protocol.

6. Continuation or Resumption of Study Treatment:

Study treatment may continue in asymptomatic subjects who do not meet the discontinuation rules, however, the investigator/site must adhere to the blood sampling and contact with Medical Monitor schedule in Table 3.

For subjects resuming treatment after an interruption of less than 7 days, the blood sampling schedule in Table 3 should be followed. In case treatment is resumed after interruption of more than 7 days, resumption of treatment must be discussed with and approved by the sponsor medical monitor. In these cases, follow-up blood sampling should occur weekly for the first month and thereafter Table 3 should be followed. Dosages should be at the same level as before the interruption.

7. Characterization of T-cell Response in Subjects Previously Treated with atabecestat

Additional blood draws of 120 mL may be taken from subjects with elevated hepatic enzymes for PBMCs to be isolated and used in an optional immunologic sub study (see Attachment 4).

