2.6.4. Biomarker Analysis Sets

The CSF A β analysis set includes all randomized subjects with valid CSF A β data at baseline and at ≥ 1 post-baseline visit. All CSF A β values will be blindly reviewed for qualification.

The amyloid PET analysis set includes all randomized subjects with valid amyloid PET data at baseline and at ≥ 1 post-baseline visit.

The CSF p-tau and t-tau analysis set includes all randomized subjects with valid CSF p-tau and t-tau data at baseline and at ≥ 1 post-baseline visit.

The tau PET analysis set includes all randomized subjects with valid tau PET data at baseline and at ≥ 1 post-baseline visit.

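### SAP 7.2 confines every biomarker summary to subjects with at least 85% compliance, a condition absent from the sets in SAP 2.6.4, and gives no unrestricted summary alongside

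*SAP*

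**What the plan says.** SAP section 7.2 lists as biomarkers the CSF markers (amyloid-beta fragments, p-tau and t-tau), amyloid PET and MRI. For amyloid PET it says "The parameters of key interest are the composite region of interest (ROI) SUVR and regional SUVR's", and for MRI "The parameters of key interest are brain volumes of the cortical and sub-cortical regions". A single sentence then governs all of them: "Biomarker analyses will be based only on those subjects with at least 85% treatment compliance", with compliance judged as of each analysis time point. Values and changes are to be summarised by arm and time point.

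SAP section 2.6.4 sets out who belongs to the biomarker sets. "The amyloid PET analysis set includes all randomized subjects with valid amyloid PET data at baseline and at" one or more post-baseline visits. The CSF amyloid-beta and CSF tau sets have the same form, and none mentions compliance. Protocol section 11.7 says "Amyloid PET analysis will be performed using the amyloid PET analysis population", makes the matching statement for CSF, and adds that the treatment effect will be estimated against placebo. Section 7.2 does not refer to section 2.6.4 or say which rule governs.

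Three other provisions bear on the point:

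- SAP section 4.3 defines compliance as days on drug divided by total treatment duration, with days off drug kept in the denominator. For subjects who stay in the study after stopping drug, the count ends at the last dosing day.
- SAP section 3.1.1 also used an 85% criterion for the CSF interim analysis. If few subjects met the criteria, that analysis was to be repeated on everyone with a result.
- Protocol Attachment 3, item 6, on raised liver enzymes, provides for resumed treatment with the medical monitor's agreement: "In case treatment is resumed after interruption of more than 7 days, resumption of treatment must be discussed with and approved by the sponsor medical".

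**The concern.** Compliance is observed after randomization, so selecting on it can make the arms differ in ways that randomization had prevented. Selection of this kind suits a target-engagement question: how far amyloid-beta falls when the drug is taken. It suits amyloid PET, CSF tau and brain volume less well, because the objectives for these markers concern the effect of atabecestat (for CSF tau and brain volume, explicitly against placebo).

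The filter could also depend on arm. Elevated liver enzymes are an identified adverse drug reaction (Protocol section 12.3.4). Protocol section 1.4 reports 11 subjects above three times the upper limit of normal in studies longer than one month: 9 on active drug, 1 on placebo and 1 blinded. If long interruptions follow such elevations, they may fall mainly on the active arms.

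Two practical matters follow. A programmer cannot tell from the SAP whether section 2.6.4 or section 7.2 defines the analysed subjects. And the PACC analysis in SAP section 5.2 has no compliance filter, so the plots in section 7.2 that set biomarkers beside cognitive change could rest on different subjects.

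**Working it through.** The plan states no figure to reproduce here. The check is which interruptions trigger the rule, and what size of distortion is plausible.

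**Inputs.** The compliance formula is from SAP section 4.3. Target days are from SAP Table 1: Month 6 = 183, Month 12 = 365, Month 24 = 729. Compliance at a time point is read as running from first dose to that target day, which SAP section 7.2 implies but does not spell out.

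**Step 1: days off needed to fail.** With k days off by day d, compliance = 100 × (d − k)/d.

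| Visit | Largest k that passes | Smallest k that fails |
|---|---|---|
| Month 6 | 27: 156/183 = 85.2% | 28: 155/183 = 84.7% |
| Month 12 | 54: 311/365 = 85.2% | 55: 310/365 = 84.9% |
| Month 24 | 109: 620/729 = 85.05% | 110: 619/729 = 84.9% |

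**Step 2: which events trigger the filter.**

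- A 7-day interruption leaves 176/183 = 96.2% at Month 6 and 358/365 = 98.1% at Month 12, so the subject stays in.
- A permanent stop on day 60 with no earlier gap gives 60/60 = 100%, because the count ends at the last dose. The subject stays in.
- Only interruptions that are later resumed and reach the totals in step 1 exclude a subject.

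**Step 3: stability across visits.** A 28-day interruption excludes at Month 6 (84.7%) but not at Month 12 (337/365 = 92.3%). A 60-day interruption excludes at Month 12 (305/365 = 83.6%) but not at Month 24 (669/729 = 91.8%). Means plotted over time can therefore rest on changing subjects.

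**Step 4: possible size, on assumed rates.** If a share e of an arm is excluded and the excluded differ from the retained by g SD, the retained mean differs from the full mean by e × g. The between-arm difference then shifts by (e_active − e_placebo) × g. The documents give neither e nor g, so these are assumptions:

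- e = 2% and 1%, g = 0.25: 0.01 × 0.25 = 0.0025 SD
- e = 5% and 1%, g = 0.5: 0.04 × 0.5 = 0.02 SD
- e = 10% and 2%, g = 1.0: 0.08 × 1.0 = 0.08 SD

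**Step 5: against sampling error.** SAP section 1 gives 557 randomized, of whom 447 had 12 months of treatment or less, leaving 557 − 447 = 110 with more. If all 557 had data (about 186 per arm), the standard error of a between-arm difference is √(2/186) = 0.10 SD. For the 110 (about 37 per arm) it is √(2/37) = 0.23 SD. The middle case of 0.02 SD is about a fifth and a tenth of these. The most extreme case of 0.08 SD is about three quarters and a third. CSF and PET were taken in subsets, so their standard errors are larger still.

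**The case against.** The strongest reply is that the liver route is narrow. The liver rules in Protocol section 10.2 and Attachment 3 are mainly rules for discontinuing treatment, and under SAP section 4.3 a permanent stop does not lower compliance. Protocol section 9.1.3 limits interruptions to significant events and asks for re-initiation as soon as possible. The 11 elevations in Protocol section 1.4 came from more than 200 subjects, under 5.5% overall (11/200). Those figures pool doses and placebo without arm denominators. This stands: only long, resumed interruptions matter, and they are probably few.

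It can also be said that section 2.6.4 sets data eligibility and section 7.2 adds a filter at each time point, as section 3.1.1 did for the interim analysis. That is a fair reading of the structure. But section 3.1.1 names the set it filters and has a route back to all subjects with a result; section 7.2 does neither.

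Two further replies stand in part. The section 2.6.4 sets themselves require a valid post-baseline value, so using them removes one selection step without giving a full as-randomized comparison. And the amended SAP names no primary estimand, analyses even PACC on treatment, and treats every comparison as exploratory. That lowers what is at stake but does not justify a compliance filter on markers of treatment effect.

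**Conclusion.** The point holds as a modest improvement to the SAP. Section 7.2 applies a post-randomization compliance filter to CSF, amyloid PET and brain volume. The CSF and amyloid PET sets and Protocol section 11.7 carry no such condition, and there is no unrestricted summary. Under the section 4.3 formula the filter acts at 28 days off by Month 6 and 55 by Month 12, and only when drug is resumed.

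A reader might infer more, and the documents do not support it:

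- That subjects taken off drug for liver enzymes drop out of the biomarker summaries. A permanent stop without earlier gaps leaves compliance at 100%.
- That section 7.2 overrides a defined set for brain volume. Section 2.6.4 defines no MRI set, so the rule fills a gap there.
- That tau PET is affected. It has a set in section 2.6.4 but is not among the biomarkers listed in section 7.2; the tau point concerns CSF p-tau and t-tau.
- That a confirmatory result is compromised, or that a material bias has been shown. Dosing has stopped, no formal testing is planned, and the section 7.2 outputs are descriptive. The range of 0.0025 to 0.08 SD rests wholly on assumed exclusion rates and differences.

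The number excluded cannot be derived from the documents, and an excess on active drug is plausible but not demonstrated.

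**What to change.** In SAP section 7.2, base the main CSF and amyloid PET summaries on the sets in section 2.6.4. Add to section 2.6.4 an MRI volume set, covering all randomized subjects with a valid baseline and at least one valid post-baseline volumetric MRI, and use it for brain volume. Keep the subset with at least 85% compliance as a labelled supportive summary for CSF and plasma amyloid-beta, where the question is target engagement.

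The cost is SAP wording and an extra amyloid-beta table. The amyloid-beta reduction in the full set may look slightly smaller than in the compliant subset.

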7.3. Pharmacokinetic/Pharmacodynamic Relationships

No analysis is planned for PK/PD relationships,

8. HEALTH ECONOMICS AND HEALTH OUTCOMES

Only on-treatment analyses will be performed for health economics and health outcomes.

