### **Exploratory Objectives**

The exploratory objectives of this study are the following:

- To investigate the effect of atabecestat compared with placebo on brain volume as measured by volumetric magnetic resonance imaging (MRI).
- To investigate the impact of atabecestat compared with placebo on markers of synaptic dysfunction on task-free functional MRI.
- To assess the effects of atabecestat on additional downstream markers of neuronal injury, neurodegeneration, or inflammation in CSF compared with placebo.
- To assess the effects of atabecestat on progression of tau spreading pathology in the brain as measured by tau PET imaging.
- To explore if baseline markers of neurodegeneration (eg, volumetric MRI, CSF t-tau or p-tau, or tau PET) are related to cognitive decline and response to treatment with atabecestat.
- To explore the correlation between the effect of atabecestat on biomarkers (eg, amyloid PET, plasma A $\beta$ , CSF A $\beta$  and t-tau or p-tau, tau PET) and clinical outcomes.
- To explore the impact of disclosure of amyloid status on questionnaires probing subject perception of amyloid imaging and concern about developing AD dementia.
- To investigate the effect of atabecestat compared with placebo on cognition as measured by a computerized cognitive battery.
- To investigate the effect of atabecestat compared with placebo on function as measured by the Financial Capacity Instrument (FCI).
- To investigate the effect of atabecestat compared with placebo on medical resource utilization as measured by the Healthcare Resource Utilization Questionnaire (HRUQ) scale.
- To investigate the effect of atabecestat compared with placebo on health outcomes as measured by the Short Form-36 (SF-36) and European Quality of Life-5 Dimensions 5-level (EQ-5D-5L) scales.
- To explore the ability of the Cognitive Function Index-acute (CFI-a) to measure decline of cognitive function and performance of everyday activities.
- To explore the effect of atabecestat compared with placebo on instrumental activities of daily life (IADL) as measured by the Amsterdam IADL questionnaire (A-IADL-Q).

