## **9. STUDY EVALUATIONS**

### **9.1. Study Procedures**

#### **9.1.1. Overview**

The Time and Events Schedule summarizes the timing of efficacy, PK, biomarker, genomic, and safety measurements applicable to this study.

The Time and Events Schedule lists the month associated with each visit during the double-blind treatment phase. During this phase, subjects will visit the site at approximately every 2 weeks for the first 3 months (visit 2 weeks=2 weeks post-Day 1, visit Month 1=4 weeks post-Day 1, visit Month 1+2 weeks=6 weeks post-Day 1, Month 2=8 weeks post-Day 1, Month 2+2weeks=10

weeks post-Day 1, Month 3=13 weeks post-Day 1), monthly intervals from 3 months to 6 months (visit Month 4=17 weeks post-Day 1, Month 5=21 weeks post-Day 1, Month 6=26 weeks post-Day 1), with additional visits at Month 8, Month 9, Month 10, and Month 12 (Month 8=34 weeks post Dose-Day 1, Month 9=39 weeks post-Day 1, Month 10=43 weeks post-Day 1, Month 12=52 weeks post-Day 1), and then at 3-month (13-week) intervals through Month 54 (eg, visit Month 15=65 weeks post-Day 1, Month 54=234 weeks post-Day 1). A visit window of  $\pm 4$  calendar days will be allowed for visits at Months 1 and 2 of the double-blind treatment phase, while a visit window of  $\pm 12$  calendar days will be allowed for subsequent visits during this phase. All visits of the double-blind treatment phase are in principle single day visits, however, they may be performed over multiple days within the allowed visit window in the case of logistical issues or subject preference. The date of the visit should always be calculated from the baseline visit, not from the prior visit.

The time points for safety measures, PK measures, and biomarker measures may be changed by the sponsor (with or without affecting the overall frequency of these assessments) prior to and during the study based on newly obtained data (eg, IA results) to optimize evaluation of the safety, PK, and PK/PD profile of the study drug. These modifications may result in a change in the overall frequency of the safety measures or sample collections. The maximal total blood volume collected per subject will not be exceeded. In general, such modifications to the time points for key study parameters, where performed only to optimize evaluation of the actual safety, PK, or PK/PD profile of atabecestat will be documented in a note to file and included in the next following protocol amendment.

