## **9.8. Medical Resource Utilization and Health Outcomes**

### **9.8.1. Healthcare Resource Utilization Questionnaire**

The HRUQ questionnaire tracks utilization of healthcare resources (excluding scheduled study visits) throughout the course of the study, and will be administered at screening and at specified visits during the double-blind treatment phase (and at ET visit, if applicable). The baseline measure captures resources utilized within the previous 6 months. The study visit measure captures resources used since the last study visit. The items measured in both versions include hospitalizations, emergency room visits, day hospitalizations, use of adult day centers, outpatient treatment, daily living arrangements, and productivity.

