2.4. Visit Windows

As subjects do not always adhere to the protocol visit schedule, the following rules are applied to assign actual visits to analysis visits. Listed below are the visit windows and the target days for each visit. The same definitions will apply to visits before or after the treatment end date using the Analysis Day as defined in Section 2.3 above. The time period description will be appended with '(On-Trt)' for post-baseline visits on or prior to the treatment end date. The time period description will be appended with '(Off-Trt)' for post-baseline visits after the treatment end date. If a subject has 2 or more actual visits in one visit window, the visit closest to the target day will be used as the protocol visit for that visit window. The other additional visit(s) will not be used in the summaries or analyses but they can be used for determination of clinically important endpoints. If 2 actual visits are equidistant from the target day within a visit window, the later visit will be used.

All assignments will be made in chronological order. Once a visit date is assigned to a visit window, it will no longer be used for a later time point except for the endpoint. Listed below (Table 1) are the visit windows and the target days for each visit defined in the protocol.

Table 1: Visit Windows for on and off-treatment Analysis

Scheduled Visit Number	Time period (label on output)	Time Interval (Day*)	Target Time Point (Day)
7	Baseline	-120 to 1	1
8	Week 2	2 to 22	15
9	Week 4	23 to 36	29
10	Week 6	37 to 50	43
11	Week 8	51 to 64	57
12	Week 10	65 to 81	71
13	Month 3	82 to 106	92
14	Month 4	107 to 134	120
15	Month 5	135 to 165	148
16	Month 6	166 to 211	183
17	Month 8	212 to 256	239
18	Month 9	257 to 288	274
19	Month 10	289 to 333	302
20	Month 12	334 to 410	365
21	Month 15	411 to 501	456
22	Month 18	502 to 592	547
23	Month 21	593 to 683	638
24	Month 24	684 to 774	729
25	Month 27	775 to 865	820
26	Month 30	866 to 956	911
27	Month 33	957 to 1047	1002
28	Month 36	1048 to 1138	1093
29	Month 39	1139 to 1229	1184
30	Month 42	1230 to 1320	1275
31	Month 45	1321 to 1411	1366
32	Month 48	1412 to 1502	1457
33	Month 51	1503 to 1593	1548
34	Month 54	1594 to 1684	1639
	Month >54	1685 to ∞	1685

* Relative to analysis reference start date if visit date is prior to or on the treatment end date. Relative to treatment end date if visit date is after treatment end date.

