8.3. Healthcare Resource Utilization Questionnaire (HRUQ)

A Healthcare Resource Utilization Questionnaire (HRUQ) will be administered during screening, after randomization at Months 1, 2, and 3, and then every 3 months through Month 54 (or early termination). At each visit whether or not a subject was hospitalized, visited an emergency room (ER), required the service of a day hospital, required the service of an adult day center, or had an outpatient consultation related to the subject's disease or treatment since the subject's last visit (or in the previous 6 months for the screening visit) will be recorded. Additional information about each healthcare resource utilized will be collected:

- Hospitalizations: Type of hospital, type of ward, reason for hospitalization (psychiatric, neurologic, social reason, or other medical reason), and start and end dates.
- ER visits: Reason for visit (psychiatric, neurologic, social reason, or other medical reason) and date of visit.
- Day hospital: Type of hospital, frequency/week, reason for visit (psychiatric, neurologic, social reason, or other medical reason), and start and end dates.
- Adult day center: Frequency/week, reason for visit (psychiatric, neurologic, social reason, or other medical reason), and start and end dates.
- Outpatient consultation related to the subject's disease or treatment: Kind of healthcare professional consulted (psychiatrist, neurologist, home care nurse, primary care physician, social worker, personal care assistant, other) and number of consultations.

The number and percentage of subjects with any healthcare resource use and with each type of healthcare resource use in the recall period will be summarized at each time point by treatment group. The number and percentage of subjects with new hospitalizations (with a start date after the previous visit) will be summarized at each time point by treatment group. Number of ER visits, frequency of use of a day hospital, frequency of use of an adult day center, and number of outpatient consultations will be summarized at each time point with descriptive statistics by treatment group.

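### Resource use is summarised only from visits on or before the last dose, but the HRUQ looks back from each visit, so nearly every subject's final on-drug interval is left out

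*SAP*

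**What the plan says.** The restriction in SAP 8 ("Only on-treatment analyses will be performed for health economics and health outcomes") covers the HRUQ in 8.3 and the accommodation and occupation items in 8.4. SAP 2.4 attaches the on-treatment label "for post-baseline visits on or prior to the treatment end date" and the off-treatment label "for post-baseline visits after the treatment end date". There is no grace period, and the date of the event plays no part.

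The HRUQ is retrospective. Protocol 9.8.1 says: "The study visit measure captures resources used since the last study visit". SAP 8.3 uses the same look-back and tabulates by visit time point. For hospital stays it collects "reason for hospitalization (psychiatric, neurologic, social reason, or other medical reason), and start and end dates". It also collects a visit date for emergency room (ER) visits, and start and end dates for day hospital and adult day centre use. Outpatient consultations are recorded only as a count.

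Protocol 11.9 planned HRUQ summaries at every scheduled time point and did not restrict them to on-treatment visits. The protocol's exploratory objective is "To investigate the effect of atabecestat compared with placebo on medical resource utilization as measured by the Healthcare Resource Utilization Questionnaire (HRUQ) scale".

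**The concern.** A visit-date rule suits a measure of how the subject is on the day. It does not suit one that reports what has happened since the last visit. The HRUQ completed just after the last dose describes an interval that began on drug, yet the rule labels the whole record off-treatment and SAP 8 then leaves it unanalysed.

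Two kinds of on-drug resource use are lost. One is the final part-interval of subjects who stop between HRUQ visits, which includes those stopped by the sponsor on 17 May 2018. The other is an admission that itself leads to stopping: it is kept if dosing continues to the next HRUQ visit and lost if dosing stops first. The second loss depends on the outcome, so it could differ between arms.

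The SAP deals with the timing problem elsewhere. Section 5.3.2 has a recall-overlap rule for the Cognitive Function Index (CFI). The adverse event part of Section 6 classifies events by onset date, through 7 days after the last dose. Sections 5 and 6 also provide off-treatment summaries. Section 8 does none of these.

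**Working it through.** **Tracing one record (illustrative days).** A subject is admitted on Day 150, takes the last dose on Day 155 and completes the Month 6 HRUQ on its target, Day 183.
- SAP 2.4: Day 183 is after the treatment end date, so the record is off-treatment. Its analysis day is 183 − 155 + 1 = 29, which falls in the Week 4 off-treatment window (Days 23 to 36).
- SAP 8: the record is not analysed.
- SAP 6: an adverse event with onset on Day 150 is treatment-emergent.
- Had dosing continued to Day 183, the same admission would count at Month 6 on-treatment.

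**Size of the gap: inputs.**
- HRUQ at Months 1, 2 and 3, then every 3 months (SAP 8.3). The target days are 29, 57 and 92, then every 91 days (SAP 2.4 Table 1; Protocol 9.1.1, "then at 3-month (13-week) intervals through Month 54").
- 557 subjects were randomised. 447 had 12 months of treatment or less and none had more than 27 months (SAP 1), which leaves 557 − 447 = 110 with more than 12 months.
- The SAP's context figures reproduce: 557/1650 = 33.8% (SAP 34%) and 447/557 = 80.3% (SAP 80%).
- Assumptions not in the documents: visits fall on target, and the last-dose day is uniform on Days 1 to 364 in the first band and Days 365 to 819 in the second.

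**Formula.** Days lost = last-dose day − latest HRUQ day on or before it.

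| Last-dose day | Mean days lost | Maximum | Share of on-drug time |
|---|---|---|---|
| 29–91 | 15.4 | 34 | 25.7% |
| 92–182 | 45 | 90 | 32.8% |
| 183–364 | 45 | 90 | 16.5% |
| 365–546 | 45 | 90 | 9.9% |
| 547–819 | 45 | 90 | 6.6% |
| 1–364 (all) | 37.5 | 90 | 20.5% |

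A subject who stops before Month 1 loses essentially the whole exposure.

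**Combining the bands.**
- Mean exposure: (1 + 364)/2 = 182.5 days and (365 + 819)/2 = 592 days.
- Lost: 447 × 37.5 + 110 × 45 = 21,712.5 person-days, or 21,712.5/557 = 39 days per subject.
- Total on drug: 447 × 182.5 + 110 × 592 = 146,697.5 person-days.
- Share: 21,712.5/146,697.5 = 14.8%.

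A simulation of the same uniform shape gave 14.9%. Two other assumed exposure shapes gave 15.2% and 16.7%, with mean losses of 39 to 45 days across the three.

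**How many subjects.** Past Month 3, about 1% of last-dose days coincide with an HRUQ day (1 in 91). Nearly every subject therefore loses a final interval, but not all do.

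**The case against.** The strongest reply is that little rests on these tables. SAP 1 says that the study objectives can no longer be evaluated, SAP 1.3 rules out formal testing, and the HRUQ receives only descriptive summaries. Hospitalisations are, with limited exceptions, serious adverse events (Protocol 12.3.2), and SAP 6 tabulates those by onset date and again for the off-treatment period. All of this stands. It limits the importance of the point but does not make the on-treatment HRUQ counts right.

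A reader might infer that the rule biases the comparison in favour of atabecestat, because raised liver enzymes are an identified adverse drug reaction with mandatory stopping rules. The documents do not support that. The rules in Protocol 10.2 are based on laboratory values, alone or with symptoms, and hospitalisation is not a criterion. Protocol 1.4 reports 11 subjects above 3 times the upper limit of normal (9 active, 1 placebo, 1 blinded), none with related symptoms. No rate of admissions leading to stopping is given for any arm.

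A reader might also take the 15% as a measure of bias. It is not. The summaries are mainly percentages and descriptive statistics at each time point, not rates per person-time, so an excluded record also leaves the denominator. Most of the 15% should come from a stop that applied to all arms at once, although the documents do not say how many subjects were already off drug.

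Nor is every stopping-related admission lost. It is kept if an HRUQ is completed on or before the last dose, or if treatment is resumed, which Protocol 9.1.3 allows.

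**Conclusion.** The point holds as a fault in how on-treatment resource use is counted. For nearly every subject, on-drug use after the last on-treatment HRUQ is excluded, and nothing in SAP 8 recovers it. The gap is about 15% of on-drug person-time (15% to 17% over the three assumed exposure shapes), given on-target visits.

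That figure measures incompleteness and should be largely non-differential. The outcome-dependent part may differ by arm, but its size and direction are unknown. No inferential result changes.

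The figure counts the whole time back to the previous HRUQ. Where a study visit without an HRUQ falls in between, a literal look-back to the last study visit would cover less, and the fix would recover correspondingly less.

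**What to change.** In SAP 8 and 8.3:

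1. **Dated events** (hospitalisations, ER visits, day hospital, adult day centre): classify as on-treatment when the recorded start or visit date is on or before the last dose. Take them from every completed HRUQ, including the first off-treatment and early-termination HRUQ. Place each in the time window given by its study day from first dose, and add an overall on-treatment count per arm.
2. **Undated items** (outpatient consultations, and the accommodation and work items in 8.4): keep the on-treatment summary as planned. Report the first post-dose HRUQ separately, labelled as an interval that straddles the last dose. It should not be moved into the on-treatment summary: past Month 3, under the uniform assumption, it holds about 45 on-drug days and 91 − 45 = 46 off-drug days.
3. Amend the SAP 8 sentence to allow both.

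The cost is a change of wording and a small change to the derivation, since SAP 8.3 already collects these dates. Coverage is limited to HRUQs actually completed after stopping: Protocol 10.2 and footnote b of the Time and Events Schedule allow assessments other than primary and secondary outcomes to be reduced in subjects off drug. The number of subjects with no post-dose HRUQ should be shown by arm.
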